10 COMPLIANCE

Treatment compliance will be calculated based on the drug exposure records captured in eCRF and summarized for the safety analysis population.

The total amount of study drug taken will be calculated from the data collected on the drug dispensation CRF during the study. The total planned study drug intake (planned dose) will be calculated as the doses planned in corresponding treatment duration.

Percentage compliance will be derived from the total amount of study drug intake divided by the planned study drug intake, and multiplied by 100%:

$$\text{Treatment Compliance} = 100 \times \frac{\text{Total Drug Taken}}{\text{Total Planned dose}}$$

, where planned dose is the protocol-specified dose which changes when subjects change/switch dose, and total drug taken takes into account any units left in the syringe.

Treatment compliance will be calculated and summarized by cohort and overall in the initial 6-month period. In the extension period, it will be calculated for each dose level a patient has ever taken and summarized by dose level for all cohorts combined. In the entire study period, it will be summarized by dose level for all cohorts combined, and by cohort and overall.

11 EXTENT OF EXPOSURE TO STUDY DRUG

For each of the initial 6-month, the extension period, and entire study period, total duration of study drug exposure, mean daily dose received ($\mu\text{g}/\text{kg}$), number of subjects who missed at least one dose, and number of days subjects missed at least one dose (for subjects who missed at least one dose) will be presented using descriptive statistics such as n, mean, SD, median, minimum, and maximum.

The number and percentage of subjects who permanently discontinue study drug during the initial 6-month period, the extension period, and entire study period will be provided along with the reason for study drug discontinuation.

The summaries will be presented for each cohort and overall in the initial 6-month period by dose level in for the extension period, and by dose level, by cohort, and all cohorts combined. [REDACTED]

12 EFFICACY EVALUATIONS

Efficacy analysis will be carried out for the initial 6-month period and the entire study period. Figures are reported on the efficacy populations. Summary tables and figures include assessments at 12 months and 6 months prior to screening (-12M and -6M Visits in Study 111-901). [REDACTED]

Some growth parameters were only optional to collect. These parameters are not included in the figures due to the sparse data. They are indicated in the tables [REDACTED]

The mean (or the non-missing measurement in case one of the two measurements is missing) of the two measurements recorded on the anthropometric measurements in the eCRF at each scheduled visit based on analysis windows will be used for the outputs/figures [REDACTED]

All assessments collected during the study are included in the outputs even if they occur following treatment discontinuation

The baseline annualized growth velocity (AGV) is established in the natural history study of Study 111-901, based on the standing height measurements in the 6 months prior to the screening visit of Study 111-202. For all other efficacy endpoints, the Baseline is defined as the last non-missing assessment prior to the first dose of study drug. Unless otherwise specified, efficacy analyses will be performed using available data at derived visits.

In the initial 6-month period, efficacy data will be summarized (absolute measures and change from baseline) by cohort and overall. With the exception of AGV, summaries include measurements from all scheduled assessments. Separate tables with testing are provided just for Day 183 including baseline just for those with assessment at Day 183.

In the entire study period, efficacy data will be summarized for Cohort 3 and Cohort 4 by cohort and Cohort 3 and 4 combined. Summaries include assessments from 12 months prior to screening (-12M Visit in Study 111-901) to up to the Month 24 Visit in study 111-202.

For Cohort 1 and 2 subjects who were switched to 15µg/kg dose level, the endpoints will be summarized by descriptive statistics at -12M, -6M, Baseline, Day 183, the first visit a patient was switched to 15µg/kg as well as the first visit with at least 6 months, and 12 months on 15µg/kg per cohort, and Cohort 1 and 2 combined. Absolute measures and changes from baseline, or change from first visit a patient was switched to 15µg/kg (as applicable), are provided. It is important to note that since the time when the subjects switched doses differs the interpretation of the summaries of data for subjects who switch should be considered with caution.

For all parameters, figures by cohort summarizing the means and SDs are provided for the visits included in the summary tables.

Exploratory testing

P-values and 95% confidence intervals for the change between baseline and the post-treatment assessment (i.e. calculated as post-treatment-baseline) will be provided for the endpoints AGV, height Z-score and body proportions at the Month 6, Month 12, Month 18 and Month 24 visits. No testing is performed for the cohort 1 and 2 switcher assessments.

All p-values will be considered descriptive and no adjustment for multiplicity will be made.

The p-values are derived from the two-sided paired t-test on the following pair of hypotheses:

H0: Change from baseline = 0

H1: Change from baseline ≠ 0

12.1 Primary Efficacy Endpoint

No primary efficacy endpoint is planned for this study.

12.2 Secondary Efficacy Endpoints

12.2.1 Annualized Growth Velocity

Annualized growth velocity (AGV) is defined as follows:

$$\text{AGV (cm/yr.)} = \frac{\text{Height at the End of the Interval (cm)} - \text{Height at the Beginning of the Interval (cm)}}{\text{Interval Length in Days}} \times 365.25$$

Where the interval length in days is calculated as interval end date – interval start date.

The interval for the calculation of the baseline AGV starts on the day of the visit in Study 111-901 that is 6 months prior to the date of the screening visit in study 111-202 and ends on the date of the screening visit in Study 111-202. A sensitivity analysis is included that considers baseline AGV derived over the 12 months prior to screening.

The AGV based on the interval between baseline and the current visit will be summarized at each 6 months (absolute and change from baseline) using descriptive statistics (mean, SD, median, 25th and 75th percentiles, minimum, and maximum).

In addition, the AGV based on the 6-month intervals will be summarized whereby AGV at each post-baseline visit is derived over the previous 6 month interval.

E.g. AGV at (Day 183 to Month 12) = ((Height at Month 12 Visit – Height at Day 183 Visit)/ (Date of Month 12 Visit – Date at Day 183 Visit)) x 365.25.

For Cohort 1 and 2 switchers the assessments do not include AGV 1st visit on 15 µg/kg.

Figures by cohort, summarizing the means and SDs, are provided for the visits included in the tables.

In addition, figures include by cohort scatter plots at each 6 month visit by age, sex and Tanner stage at the visit (genital for males/breasts for females), dot plots for baseline versus post-baseline assessment and individual spaghetti plots.

Cohort 3 and 4 AGV plots over the entire study period, (AGV from baseline and 6-month intervals). For Cohort 1 and 2 switchers, the mean (+/- SD) AGV at baseline, the 1st visit with at least 6 months, and 12 months on 15µg/kg will be plotted by cohort.

12.2.2 Key Growth Measures

Key growth measures include:

- Standing Height (cm)
- Sitting Height (cm)
- Lower Body Length (cm) – calculated as [Standing Height – Sitting Height]
- Upper Arm Length (cm)
- Lower Arm (Forearm) Length (cm)
- Upper Leg Length (Thigh) (cm)
- Tibial Length (cm)
- Knee to Heel Length (cm)

Summary tables and figures are provided as described above in Section 12.

A further figure of individual subject data is included: Spaghetti Plot of Standing Height with Age-Specific Non-ACH and ACH References by Cohort and Sex (in initial 6 month period, and entire study period).

12.2.3 Height and Weight Z-Scores

Height and weight will be converted to age-and sex-appropriate standard score (SDS), also referred to as Z-score, by comparison with normal reference standards (non-ACH) from the Centers for Disease Control and Prevention (CDC) database.

Summary tables and figures are provided as described above in Section 12.

Further figures of individual subject data are also included:

- Height Z-Scores Using Non-ACH References over Age Prior to Treatment (BMN111-901) and in Entire Study Period – Cohort 3 and 4
- Change from Baseline in Height Z-Scores Using Non-ACH References over Age by Subject and Cohort – Cohort 3 and 4
- Change from Baseline in Height Z-Scores Using Non-ACH References over Age by Subject and Cohort – Cohort 1 and 2 switchers

12.2.4 Body Proportions

The following body proportion ratios are assessed (* optional):

- Upper to Lower Body ratio: $\text{Sitting Height} / (\text{Standing Height} - \text{Sitting Height})$
- Upper Arm Length to Lower Arm (Forearm) Length ratio: $\text{Upper Arm Length} / \text{Lower Arm (Forearm) Length}$
- Upper to Lower Leg ratio:
 - $\text{Upper Leg Length (Thigh)} / \text{Knee to Heel Length}$

- Upper Leg Length (Thigh)/ Tibial Leg Length
- Arm Span* to Height ratio: Arm Span / Standing Height

Summary tables and figures are provided as described above in Section 12.

12.2.5 Other Growth Measures

Some other growth measures are also summarized (* are optional):

- Arm span (cm) *
- Weight (kg)
- BMI (kg/m²)
- Head Circumference (cm)
- Head Length (cm) *
- Foot: Length and Width (cm)
- Waist Circumference (cm) *
- Hand: Palm Length, Middle Finger Length, and Palm Width (cm)
- Chest: Mid-expiration, Maximum Inspiration, and Maximum Expiration (cm) *

Summary tables and figures are provided as described above in Section 12.

In addition to the summaries and figures described above, the further figure is included:

- Spaghetti Plot of Weight with Age-Specific Non-ACH References by Cohort, Sex in initial 6 month period, and entire study period.

13 EXPLORATORY ANALYSIS

13.1 Biomarker Analysis

Biomarkers assessed are (C-terminal cross-linked telopeptide of type II collagen [CTX-II]), chondrocyte and osteoblast activity (bone-specific alkaline phosphatase [BSAP]), bone formation (pro-collagen Type 1 N-terminal propeptide [PINP]), osteocalcin; and markers of BMN 111 activity (cyclic guanosine monophosphate [cGMP], N-terminal propeptide of C-type natriuretic peptide [NT-proCNP], and atrial natriuretic peptide [ANP]).

CTXII, BSAP, PINP and Osteoblast will be evaluated by value and change from baseline to each scheduled visit. and cGMP, NT-proCNP, and ANP are assessed at the pre-dose and post dose assessment.

Tables will be summarized on the safety population by cohort and all cohorts combined in the initial 6-month period by dose level in the extension period, and by dose level, by cohort, and all cohorts combined in the entire study period. Figures will be summarized by cohort in the initial 6-month period, by dose level in the extension period, and by dose, by cohort, and all cohorts combined in the entire study period.

For CTX-II, BSAP, PINP, and osteocalcin, post-baseline assessments on the day of escalation will be summarized under the previous dose.

For cGMP, NT-proCNP, and ANP, post-baseline assessments on the day of escalation will be summarized under the new dose.

13.2 Sleep Apnea Analysis

A sleep-testing device will be used to assess the presence and severity of sleep-disordered breathing by measurement of blood oxygen saturation, pulse rate, and airflow during overnight monitoring at Screening and on Days 85 and 183 of the initial phase, and Months 12 and 24 of the optional, open-label extension phase. Assessment of sleep apnea will include, but may not be limited to, determining the number of episodes of apnea and hypopnea per hour (Apnea/Hypopnea Index, AHI). Other exploratory analysis of sleep apnea may be performed.

The full list of variables to be summarised will be described in more detail in a separate appendix.

13.3 Imaging Assessment Analysis

Exploratory imaging assessment data to be evaluated include measurements of lumbar spine, lower extremity, bone age, QCT and will be summarised for the absolute measures change from baseline and percent change from baseline using the efficacy population. Difference between estimated skeletal bone age and chronological age will be calculated and reported in a summary table. In the initial 6-month period, imaging assessment data will be summarized by cohort and overall. In the entire period, the data will be summarized by descriptive statistics at each available derived visit for Cohort 3 and 4 and Cohort 3 and 4 combined. For Cohorts 1 and 2 subjects who were switched to 15µg/kg dose level, the data will be summarized with descriptive statistics at the first visit a patient was switched to 15 µg/kg as well as the first visit with at least 6 months and 12 months on 15µg/kg by cohort and Cohort 1 and 2 combined.

Mean value of QCT, x-ray lumbar spine, lower extremity, bone age at each time point will be plotted by cohort for Cohort 3 and 4 in the entire study period. For Cohort 1 and 2 switchers, the mean value of the

same imaging assessment data at baseline, 1st visit with at least 6 months and 12 months on 15ug/kg will also be plotted by cohort.

13.4 Elbow Joint Range of Motion

The value and change from baseline in the elbow joint range of motion to each scheduled time point will be summarized using descriptive statistics (mean, SD, median, 25th/75th percentile, minimum, and maximum). Results will be summarized for the efficacy population by cohort and overall in the initial 6-month period by dose level in the extension period, and by dose level, by cohort, and all cohorts combined in the entire study period. The value of the elbow joint range of motion at each time point for each individual will be plotted by cohort for the entire study period.

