Subjects will remain on a daily fixed dose throughout the initial 6-month treatment period. Subjects in each cohort continue to receive daily dosing (Cohort 1, 2.5 µg/kg; Cohort 2, up to 7.5 µg/kg, Cohort 3, up to 15 µg/kg, and Cohort 4, 30 µg/kg) for 6 months unless stopping criteria are met. When clinical safety is established and stopping criteria are not met after all 8-10 subjects have completed at minimum their first

10 days of cohort dosing, and after DMC review and approval, the subsequent cohort may be open to enrollment.

In the 18-month optional, open-label extension period, eligible Cohorts 1 and 2 subjects were dose escalated to the 15µg/kg dose while Cohort 3 and Cohort 4 subjects continued at their respective starting doses of 15µg/kg and 30µg/kg, respectively, based on the pre-specified dose adjustment criteria described in the protocol and amendments.

Figure 2.2.1: Study Design

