3.2 Data and Cohort Presentation

All available data for study BMN111-202 will be used for the final analysis. Efficacy data collected in study BMN111-901 that is 12 months prior to screening in BMN111-202 for subjects who subsequently enrolled in study BMN11-202, and are included in the corresponding analysis population, will be summarized in efficacy tables and figures.

For the initial 6-month period, unless otherwise specified, all data will be presented for each cohort and all cohorts combined.

In the extension period, efficacy and imaging assessment data will be summarized for Cohorts 1 and 2 subjects who switched to 15 μ g/kg by cohort, and Cohort 1 and 2 combined.

In the entire study period, efficacy and imaging assessment data will be summarized for Cohort 3 and Cohort 4 separately, and Cohort 3 and 4 combined.

In the extension period, all other data will be summarized by dose level and all cohorts combined. For the entire study period, unless otherwise specified, safety data are summarized by dose level, and by cohort, and all cohorts combined. Subjects in Cohorts 1 and 2 may be represented at multiple dose levels and are accounted once for each dose level they receive.

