3.4 Visit Windows for Analysis

An assessment for a subject will be classified according to the study day of the assessment where it falls within a window. The analysis windows are designated for each scheduled visit and centered on a target day. If there are two or more assessments within a designated window, the assessment that is closest to the target day will be used for analyses. If the two closest assessments to the target day are equidistant from the target day, the assessments taken on a scheduled visit per CRF page will be used.

Data in BMN111-901 for subjects who enrolled in BMN111-202 study and are included in the corresponding analysis population will be used in efficacy summary tables and figures. The analysis visits and windows for assessments in BMN111-901 are defined below in [Table 3.4.1](#). The analysis windows for assessments in BMN111-202 are defined below in [Table 3.4.2](#) for the initial 6-month period and the extension period. Unless otherwise specified, all analysis are based on derived visits.

Table 3.4.1: Visit Time Windows for Observed Assessments in BMN111-901

Derived Visit	Target Day ^a	Window ^a	
-6M	-183	-228	-138
-12M	-364	-409	-319

^aTarget days and window are relative to the Screening date from the Anthropometric CRF form in BMN111-202

Table 3.4.2: Visit Time Windows for Observed Assessments in BMN111-202

Derived Visit	Target Day ^a	Window
Initial 6-Month Period		
Baseline		The last assessment on or prior to the first dose unless otherwise specified.
Day 1	Day 1	Day 1
Day 2	Day 2	Day 2
Day 3	Day 3	Day 3
Day 4	Day 4	Day 4 – Day 7
Day 10	Day 10	Day 8 – Day 12
Day 15	Day 15	Day 13 – Day 18
Day 22	Day 22	Day 19 – Day 25
Day 29	Day 29	Day 26 – Day 36
Day 43	Day 43	Day 37 – Day 64
Day 85	Day 85	Day 65 – Day 106
Day 127	Day 127	Day 107 – Day 155
Day 183	Day 183	Day 156 – The last date of the Day 183 visit or Day 190 for subjects not entering the extension period
Extension Period (For subjects who enter extension)		
Month 8	Day 243	Day 183 Visit Date + 1 – Day 273
Month 10	Day 303	Day 274 – Day 333
Month 12	Day 364	Day 334 – Day 410
Month 15	Day 456	Day 411 – Day 501
Month 18	Day 547	Day 502 – Day 592
Month 21	Day 638	Day 593 – Day 684
Month 24	Day 730	Day 685 – the actual date of the nominal month 24 visit regardless of the analysis day

^a Target days are relative to the first dosing day.

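### In the elbow range-of-motion tables by dose level, the 15 µg/kg column includes change that Cohort 1 and 2 switchers accrued on lower doses

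*SAP*

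**What the plan says.** For elbow range of motion, SAP 13.4 states: "The value and change from baseline in the elbow joint range of motion to each scheduled time point will be summarized using descriptive statistics". On grouping it says: "Results will be summarized for the efficacy population by cohort and overall in the initial 6-month period by dose level in the extension period". The same sentence adds tables by dose level, by cohort and for all cohorts combined over the entire study period. The section ends with a plot of each child's values by cohort for the whole study.

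There is one baseline. SAP 12 says: "For all other efficacy endpoints, the Baseline is defined as the last non-missing assessment prior to the first dose of study drug". The baseline row of SAP Table 3.4.2 reads: "The last assessment on or prior to the first dose unless otherwise specified". The extension has no baseline of its own.

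SAP 2.2 records that "eligible Cohorts 1 and 2 subjects were dose escalated to the" 15 µg/kg dose in the extension, while Cohort 3 stayed at 15 and Cohort 4 at 30 µg/kg. SAP 3.2 counts Cohort 1 and 2 subjects once at each dose level they receive.

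Growth and imaging are handled differently. SAP 3.2, 12 and 13.3 keep the switchers in their own tables. SAP 12 also offers change from the first visit on 15 µg/kg, with this caution: "since the time when the subjects switched doses differs the interpretation of the summaries of data for subjects who switch should be considered with caution". Everything else falls under a general rule in SAP 3.2: "In the extension period, all other data will be summarized by dose level and all cohorts combined". Section 13.4 neither repeats nor cites the switcher scheme. Protocol 13.3.1.5 had summarised this endpoint by dose cohort only.

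**The concern.** A column headed 15 µg/kg that reports change from baseline invites the reader to take that change as the result of 15 µg/kg. For Cohort 3 this is so. For a switcher, the interval from baseline to visit contains at least 6 months on 2.5 or up to 7.5 µg/kg, and that time counts as if it were time on 15 µg/kg. If lower doses do less, the column understates what 15 µg/kg does over the stated time. If lower doses do something, that change is credited to the wrong dose.

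The endpoint is exploratory, but it has a safety use. Protocol 9.10.4 uses elbow range of motion in safety reviews, and Protocol 9.1.1.1 lists clinically significant worsening among the stopping criteria. It is also a measure on which any drug effect could build up slowly, so mixing dose and duration in one column matters more here than for a measure that follows the current dose.

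The section's status is unclear as well. Protocol 9.10.3 lists elbow range of motion as an exploratory efficacy variable, and SAP 13.4 uses the efficacy population. If it is efficacy data, 13.4 departs from the grouping in SAP 3.2. If it is other data, the pooling applies as written.

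**Working it through.** The plan gives no figure to reproduce here: no sample size calculation, effect size or SD is stated. The check is arithmetic on planned cohort sizes and visit months.

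**Inputs from the documents**
- Cohort 1: 8; Cohort 2: 8; Cohort 3: n3 = 8 to 10 (Protocol 9.1).
- Time on the starting dose before any switch: at least 6 months. The dose is fixed for the initial phase, and the first escalation rule in Protocol 9.1 needs at least 6 months of treatment, judged on all subjects in the cohort. Month 6 is therefore a floor.
- Switch times differ between subjects (SAP 12); no dates are given.

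**Assumptions, for illustration only**
- All 16 Cohort 1 and 2 children switch, together, at month s = 6, 10 or 12.
- Change is linear in time, at a rate on the lower dose equal to f times the rate on 15 µg/kg.

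**Step 1: share of switchers in the column.** w = 16/(16 + n3), which is 16/26 = 62% to 16/24 = 67%.

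**Step 2: share of a switcher's interval spent below 15 µg/kg at visit month t.** This is s/t. At Month 24 it is 6/24 = 25%, 10/24 = 42% or 12/24 = 50%. At Month 18 it is 33%, 56% or 67%.

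**Step 3: column mean relative to the change in a child on 15 µg/kg throughout.** A switcher shows (f·s + t − s)/t of that change. Averaging over the column gives

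R = 1 − w(1 − f)s/t.

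Worked cases with f = 0 and t = 24:
- s = 6: (16 × 0.75 + 8)/24 = 83%; (16 × 0.75 + 10)/26 = 85%.
- s = 12: (16 × 0.50 + 8)/24 = 67%; (16 × 0.50 + 10)/26 = 69%.

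| Switch month | Month 18, f = 0 | Month 24, f = 0 | Month 18, f = 0.5 | Month 24, f = 0.5 | f = 1 |
|---|---|---|---|---|---|
| 6 | 78–79% | 83–85% | 89–90% | 92% | 100% |
| 10 | 63–66% | 72–74% | 81–83% | 86–87% | 100% |
| 12 | 56–59% | 67–69% | 78–79% | 83–85% | 100% |

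**Step 4: sensitivity to how many switch.** SAP 2.2 speaks of eligible subjects. If only 8 of the 16 switch, w = 8/18 = 44% to 8/16 = 50%. A Month 12 switch with f = 0 then gives 1 − 0.50 × 0.50 = 75% to 1 − 0.44 × 0.50 = 78% at Month 24.

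**Step 5: with a baseline taken at the switch.** The interval becomes t − s months, all on 15 µg/kg, and the lower-dose share is zero. At Month 24 this is 18 months for a Month 6 switch and 12 months for a Month 12 switch.

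**The case against.** The strongest reply is that nothing is hidden. SAP 13.4 also gives entire-period tables by cohort and plots every child by cohort. A reader who wants the undiluted 15 µg/kg result can take it from the Cohort 3 column and compare it with Cohort 4. This stands, and it rules out the reading that a skeletal signal would be lost from the report. It does not correct the dose-level columns. Nor does it give the switchers' change since the switch, because a Cohort 1 or 2 row still measures from before the first dose and can mix children before and after their switch.

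Second, no stopping decision depends on this column. The elbow criteria in Protocol 9.1.1.1 rest on clinical assessment and goniometry in individual children, with the data monitoring committee informed or reviewing. The animal skeletal findings in Protocol 7.1 that are described in detail concern the hip. Both points stand.

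Third, a reader might infer that the column shows only about half of the true effect. A Month 12 switch read at Month 15 would give 47–51%, but that needs a late common switch, an early reading and no lower-dose effect at all. The documents supply none of these.

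Fourth, a reader might extend the point to the laboratory tests in SAP 14.2 and the biomarkers in SAP 13.1, which are also grouped by dose level. The argument needs change that accumulates with time on dose. That does not carry over to laboratory tests, and it is not clear for biomarkers that reflect the current state. For such measures, attributing a value to the current dose against a pre-treatment baseline is defensible.

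**Conclusion.** The point holds for SAP 13.4. The extension and entire-period tables by dose level attribute to 15 µg/kg some change that accrued on lower doses, in up to 62–67% of the children in that column. That composition follows from the planned sizes if all 16 switch; the size of the distortion does not follow from the documents. It depends on switch dates and lower-dose rates, neither of which is given. Under the stated assumptions the column shows 83–85% of the true change at Month 24 for a Month 6 switch and 67–69% for a Month 12 switch. It shows more if lower doses have some effect, and all of it if rates are equal.

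This is a labelling and attribution fault in a descriptive, exploratory table, with sound displays beside it. It is worth correcting because the SAP already has the remedy for growth and imaging.

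**What to change.** In SAP 13.4, for both the extension and the entire period:

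- Show the 15 µg/kg results separately for Cohort 3 (15 µg/kg from Day 1) and for Cohort 1 and 2 switchers, as SAP 12 and 13.3 already do.
- For switchers, add change from the last non-missing value on or before the first 15 µg/kg dose, at the first visit with at least 6 and at least 12 months on 15 µg/kg. Keep change from study baseline beside it.
- State the limit of that switch baseline. Elbow range of motion is measured at every scheduled extension visit but is not on the dose-adjustment visit list (Protocol Table 9.1.3 and section 11.6). After an unscheduled adjustment visit, the switch baseline may precede the switch by some weeks, which leaves a little lower-dose time in the interval.

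No new data are needed. The cost is SAP wording, one derived baseline, a switcher panel indexed by time on 15 µg/kg, and smaller columns: 8–10 children in Cohort 3 and up to 16 switchers, in place of 24–26 pooled. SAP 13.1 and 14.2 need no change on this account.
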